### **2.3.2 Intention to Treat (ITT) Analyses**

To control a possible attrition bias, intention to treat analyses will be performed using multiple imputation techniques for the imputation of missing data. The method of imputation was not defined in the first version of the analyses plan. It was defined in March 2016 after the study statistician had completed a workshop for the handling of missing data in the end of February in Stockholm (Metrika Consulting – The Nordic STATA Contributor).

#### **2.3.2.1 Definition of the Analyses Set**

The ITT analyses will be carried out on the subsample of baseline-sample with baseline data regarding the primary efficacy endpoint under consideration. Thus, individuals which dropped out during the baseline assessment before the efficacy endpoint was surveyed will be excluded from the intention to treat analyses as there is not the necessary data available to allow the imputation of the follow data.

Missing values in the follow-up variable of the primary efficacy outcome will be imputed if the baseline value is not missing. Hence the ITT analyses can be seen as partial ITT analyses. The attrition bias caused by drop-out between the measurement points will be controlled by the imputation. A possible attrition bias caused by drop-out during baseline assessment will be not controlled by the ITT analyses proposed here.

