#### **2.3.1.2 Primary efficacy Analyses**

For primary efficacy analyses, for each of the main outcome of the study a separate generalized linear mixed model is fitted with the model specification corresponding to the scale level of the outcome under investigation. Thus, for quality of life, caregiver burden and neuropsychiatric symptoms linear mixed regressions will be used assuming a Gaussian distribution, while for antidementive drug treatment and PIM prescription logistic mixed models will be used. To account for the stochastic dependency of patients treated by the same GP, the GP will be included as random effect variable.

The follow up outcome variable at  $T_1$  (twelve months after finishing the baseline) will be the dependent variable in these analyses; the study group is the predictor of interest, while the baseline value ( $T_0$ ) of the outcome variable will be included as covariate to diminish residual variance and to account for inter-individual variance at baseline. Furthermore, sociodemographic variables (age, sex and living situation (alone vs. not alone)) are planned to be included as covariates, too. These variables can be supposed to contribute proportions of variance to the outcome variables which should be independent of possible study effects as the intervention cannot change age, sex or living situation. Thus, the inclusion of these variables should result in decreased residual variance enhancing thereby

the statistical power to detect differences between study groups. A positive intervention effect is then defined as a significant regression coefficient (one-sided test) of the study group variable. The p-values will be interpreted one-sided as one-sided hypotheses are tested. The design of the DelpHi trial allows for multiple testing (five primary outcomes), therefore, additionally the Bonferroni corrected p-values will be reported.

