### **2.3.2.2 Methods of Imputation**

The imputation model will be chosen congenial to the analyses model with the difference that the GP will be included as a fixed effect in the imputation model. Thus, the model of imputation will be a linear regression for the care-giver burden, quality of live and NPI and logistic for antidementive drug use and the PIM, including the respective baseline variable, age, sex, the living status and the study group variable as predictors. The method of imputation is chosen to be multiple imputations via chained equations, using 50 runs of imputations. Standardized effect sizes will be also computed from these imputations and compared to the estimates of the per protocol analyses. Note that an important statistical pre-requisite for the usage of imputations is that the missing of the outcome variable is stochastically independent from the value of the outcome variable at follow-up given its baseline value.

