### **2.3.2.4 Sensitivity Analyses (ITT)**

The sensitivity analyses described in the per protocol analyses are not feasible using multiple imputation for computational reasons (bootstrap, random slopes). We plan, however, to use a second imputation model (predictive mean matching) for sensitivity analyses to test the dependency of the results on the concrete imputation method. Thus, we will rerun the ITT analyses only with the

difference that the imputation models (including the same variables as before) will be based on predictive mean matching. Again, 50 runs of imputations will be used.

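### For the three metric endpoints the imputation model adds no predictor to the analysis model, so the ITT analysis does little about patient-level attrition bias and cannot be said to control it

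*SAP*

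**What the plan says.** SAP section 2.3.2 gives the purpose: "To control a possible attrition bias, intention to treat analyses will be performed using multiple imputation techniques". Section 2.3.2.1 restricts imputation to missing follow-up values in people whose baseline value is present, and then says "The attrition bias caused by drop-out between the measurement points will be controlled by the imputation".

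Section 2.3.2.2 sets out the imputation model as congenial to the analysis model, with one difference: "the GP will be included as a fixed effect in the imputation model". Its predictors are stated as "including the respective baseline variable, age, sex, the living status and the study group variable as predictors". The same section names a prerequisite, that "the missing of the outcome variable is stochastically independent from the value of the outcome variable at follow-up given its baseline value", and plans a comparison: "Standardized effect sizes will be also computed from these imputations and compared to the estimates of the per protocol analyses".

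The analysis model in section 2.3.1.2 uses study group, the baseline value of the endpoint and GP as a random effect, and "sociodemographic variables (age, sex and living situation (alone vs. not alone)) are planned to be included as covariates, too". The per-protocol set is the complete cases (section 2.3.1.1). The only ITT sensitivity analysis changes the method and not the predictors: "the imputation models (including the same variables as before) will be based on predictive mean matching" (section 2.3.2.4). The drop-out regressions in section 2.4.2 concern drop-out during the baseline assessment.

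**The concern.** When only the outcome is missing, and it is imputed from the covariates that the analysis model already adjusts for, people without follow-up bring almost no new information on the treatment coefficient. The imputation then nearly reproduces the complete-case answer. The ITT analysis is the SAP's stated safeguard against attrition between the two measurements, in an unblinded trial where death and withdrawal are expected to be the main causes of missing data. If the safeguard does little for patient-level drop-out, a close match between ITT and per-protocol results could be taken as reassurance that it cannot give.

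**Working it through.** The SAP gives no figure for this point, so the main check sets the two models side by side.

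| Term | Analysis (2.3.1.2) | Imputation (2.3.2.2) |
|---|---|---|
| Study group | yes | yes |
| Baseline value of the same endpoint | yes | yes |
| Age, sex, living situation | yes | yes |
| GP | random | fixed |
| Any other variable | none | none |

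**Reasoning.** If the prerequisite in section 2.3.2.2 holds, the complete-case model is already valid because it adjusts for baseline, and the imputation has nothing to correct. If it fails at patient level, the imputed values come from the same distorted relation among completers. The exception is the GP term. A practice that loses many patients counts for less among complete cases, and imputing at that practice's own level gives back some of its weight.

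**Simulation inputs.** From section 2.5 and Table 1: 100 GPs, mean size 5, baseline/follow-up correlation 0.6, and ICC 0.061 (quality of life), 0.192 (caregiver burden) and 0.361 (NPI). The detectable differences 0.26, 0.35 and 0.43 are read as SD units (assumption). Drop-out of 25% is also assumed, because the SAP gives no rate. There were 50 imputations, combined by Rubin's rules.

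*Set A*: 1000 trials per scenario, ICC 0.061, true effect 0.26. GPs without completers (about 7%) take the arm mean. The unmodelled variable has coefficient 0.3 and log-odds of drop-out 1 per SD (assumptions).

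| Drop-out | Complete case | SAP imputation | Predictive mean matching |
|---|---|---|---|
| Random | 0.258 | 0.258 | 0.255 |
| By baseline value | 0.259 | 0.259 | not reported |
| By unmodelled variable, alike in both arms | 0.259 | 0.260 | not reported |
| By unmodelled variable, one arm | 0.191 | 0.190 | 0.188 |
| By unmodelled variable, opposite by arm | 0.131 | 0.131 | 0.129 |
| By GP effect, opposite by arm | 0.205 | 0.243 | 0.237 |

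With 15% and 35% missing, the one-arm case gives 0.214 and 0.169 for both complete case and SAP imputation.

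*Set B*: 150 trials per scenario, true effect 0.26 at each ICC, GPs without completers left out, drop-out in one arm depending on the outcome itself.

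| ICC | Full data | Complete case | Imputation | Share of bias kept |
|---|---|---|---|---|
| 0.061 | 0.265 | 0.406 | 0.397 | 0.132/0.141 = 94% |
| 0.192 | 0.264 | 0.401 | 0.389 | 0.125/0.137 = 91% |
| 0.361 | 0.277 | 0.398 | 0.386 | 0.109/0.121 = 90% |

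Further runs with outcome-driven drop-out removed about 5% (ICC 0.061) and 11% (ICC 0.361) when it acted oppositely by arm, and at most about 12% in any run.

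**GP-linked bias removed (set A).**
- ICC 0.061: about 0.038/(0.26 − 0.205) = 70%
- ICC 0.192: (0.318 − 0.272)/(0.35 − 0.272) = 59%
- ICC 0.361: (0.382 − 0.342)/(0.43 − 0.342) = 45%

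**Standard error under random drop-out.** Set A: 26%, 15% and 8% larger at the three ICCs with the arm-mean rule, and 27%, 17% and 11% larger with GPs without completers left out. Set B, ICC 0.061: 0.122/0.096 = 1.27.

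**Effect of an auxiliary variable (set A, one-arm case).** Correlations of 0.3, 0.7 and 1.0 with the cause of drop-out move the imputed estimate from 0.190 to 0.196, 0.223 and 0.259. The shares of bias recovered are 0.006/0.070 = 9%, 0.033/0.070 = 47% and 0.069/0.070 = 99%.

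**The case against.** The SAP is more careful than the one sentence suggests. Section 2.3.2.2 states the missing-data condition, section 2.3.2.1 calls the analysis a partial ITT, and section 2.4.2 speaks only of reducing the impact of drop-out. Under the stated condition the ITT estimate is valid. That stands: the analysis is then redundant, not wrong. It does not rescue the sentence, because under that condition the complete-case model needs no correction.

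A reader might infer that the two estimates are identical, or that imputation corrects nothing. That is too strong. Outcome-driven drop-out runs partly through the GP level, so a little bias is removed, and GP-linked bias is removed to a useful degree. This matters because section 2.4.3 thinks it likely that GPs differed in adherence.

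A reader might also infer that agreement between the two analyses is guaranteed. It is not. At ICC 0.061 the estimates lay within 0.05 of each other in about 90% of trials under the arm-mean rule, but in only 66 to 76% when GPs without completers were imputed at a reference GP's level. The SAP does not say which handling applies.

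Nor do the documents show that the trial suffers attrition bias. They give no drop-out rate or mechanism, and the simulated bias falls below the true effect in set A and above it in set B purely by choice of mechanism. The SAP also does not say that agreement will be read as evidence against bias; it says only that the estimates will be compared.

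Finally, chained equations could bring the other endpoints in as auxiliary variables if all were imputed jointly, but the listed predictors include only the endpoint's own baseline value.

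**Conclusion.** The point holds for the three metric endpoints; the two binary endpoints were not examined. For patient-level drop-out the planned ITT estimate is nearly equal in expectation to the complete-case estimate and less precise. Where the missing-data condition fails, both keep nearly all of the bias: all of it when an unmodelled variable drives drop-out, and roughly 90% or more (88% at the lowest) when the outcome does. GP-linked bias is the exception, with 45 to 70% removed at 25% missing. These shares rest on the assumed drop-out rate and mechanisms.

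Control of attrition bias is therefore claimed but not delivered, and neither the per-protocol comparison nor predictive mean matching with the same variables can say much about it. The complete-case analysis is not invalidated. The plan should be corrected because its stated safeguard does not do what the text says.

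**What to change.** 1. Add to the imputation model variables the trial already holds: the DEMTECT screening score, dementia severity, baseline values of the other primary endpoints, and their follow-up values where observed. They help only as far as they capture the cause of drop-out.
2. Together with (1), reword section 2.3.2.1 to say that this bias *may be reduced by the imputation as far as the variables in the imputation model explain drop-out*. After the comparison in section 2.3.2.2 add: *Agreement with the per-protocol estimates is not evidence against attrition bias.* State there how GPs without completers are imputed.
3. Extend the section 2.4.2 regressions (overall, death, withdrawal), with study group as predictor, to drop-out between baseline and follow-up.
4. Optional: a delta-adjusted analysis, with its range justified and deaths considered separately from withdrawals.

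The cost is wording, modest programming and a table or two; no new data are needed. There are limits. NPI and caregiver burden depend on a caregiver, who was enrolled only where possible, so as auxiliaries they must themselves be imputed. Follow-up values of other endpoints will mostly be missing in the same people. Follow-up data were analysed from April 2016 (section 1), so later additions must be labelled post hoc.

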### **2.3.2.2 Methods of Imputation**

The imputation model will be chosen congenial to the analyses model with the difference that the GP will be included as a fixed effect in the imputation model. Thus, the model of imputation will be a linear regression for the care-giver burden, quality of live and NPI and logistic for antidementive drug use and the PIM, including the respective baseline variable, age, sex, the living status and the study group variable as predictors. The method of imputation is chosen to be multiple imputations via chained equations, using 50 runs of imputations. Standardized effect sizes will be also computed from these imputations and compared to the estimates of the per protocol analyses. Note that an important statistical pre-requisite for the usage of imputations is that the missing of the outcome variable is stochastically independent from the value of the outcome variable at follow-up given its baseline value.

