### **2.3.2.3 Primary Efficacy Analyses (ITT)**

The ITT analyses will be performed following the schedule of the per protocol analyses with the only difference being that missing follow-up values will be imputed.

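### Imputing with GP as a fixed effect inflates the ITT standard errors of the continuous outcomes and leaves the logistic imputation model without a finite fit

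*SAP*

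**What the plan says.** The analysis model in SAP section 2.3.1.2 is a mixed model in which "the GP will be included as random effect variable". Section 2.3.2.3 carries it over: "The ITT analyses will be performed following the schedule of the per protocol analyses". Section 2.3.2.2 calls the imputation model congenial to this analysis, but "with the difference that the GP will be included as a fixed effect in the imputation model". It is linear for the three scales and "logistic for antidementive drug use and the PIM", with the baseline value, age, sex, living status and study group as further predictors.

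Section 2.3.2.1 sets the scope: "Missing values in the follow-up variable of the primary efficacy outcome will be imputed if the baseline value is not missing". Section 2.3.2.4 repeats the imputation by predictive mean matching with the same variables. Section 2.5 plans on 100 GPs with a mean of 5 patients and a coefficient of variation of 1. No section says what to do when a GP effect cannot be estimated.

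**The concern.** With about 100 GPs of about 5 patients, each GP coefficient in the imputation model rests on very few observed outcomes. Three things follow.

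- **Continuous outcomes.** The GP effects are not shrunk, so imputed values carry the estimation noise of their GP. The random-GP analysis reads this as a higher ICC and reports standard errors that are too large.
- **Binary outcomes.** A GP whose observed outcomes are all 0 or all 1 has no finite logistic coefficient. Every GP with one observed patient is in this state.
- **All five outcomes.** A GP with no observed follow-up has no estimable effect, although its patients with a baseline value are meant to be imputed.

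At stake are the ITT confidence intervals and one-sided p-values, and the promise that "additionally the Bonferroni corrected p-values will be reported". For the binary outcomes the ITT odds ratio itself depends on a choice the analyst would have to make without guidance. Study group is also collinear with the GP dummies, because GPs were randomised; that alone is harmless.

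**Working it through.** **Inputs.** From SAP section 2.5: 100 GPs, mean size m = 5, CV 1, 250 per arm, baseline to follow-up correlation 0.6, ICC 0.061 (quality of life, QoL), 0.192 (burden), 0.361 (NPI). From section 2.3.2.2: 50 imputations. Not in the SAP, so assumed: missing rates of 10 / 20 / 35%; Table 1 baseline ICCs holding for the adjusted 12-month outcome; for the binary outcomes, prevalence 25%, ICC 0.05, baseline log odds ratio 2.5, treatment log odds ratio 0.6.

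**Step 1: the SAP's own figures.** Table 1 is reproduced by d = (t₀.₉₇₅,₉₈ + t₀.₈₀,₉₈) × √(2/250 × DE × (1 − 0.6²)) with DE = 1 + (1 + CV²) × m × ICC:

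- QoL: DE = 1.61, d = 0.257 (stated 0.26)
- Burden: DE = 2.92, d = 0.346 (stated 0.35)
- NPI: DE = 4.61, d = 0.435 before rounding error (stated 0.43)

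The more usual DE = 1 + ((1 + CV²)m − 1) × ICC gives 0.252 / 0.334 / 0.417. Nothing below depends on which form was used. The SAP gives no figure for the effect of the imputation model.

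**Step 2: why the standard error rises.** In a GP with 4 observed patients, the sampling variance of an unshrunken GP effect, relative to the true between-GP variance, is (1 − ICC)/(4 × ICC):

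- QoL: 0.939/0.244 = 3.85
- Burden: 0.808/0.768 = 1.05
- NPI: 0.639/1.444 = 0.44

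The noise matters most where the true ICC is lowest.

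**Step 3: simulation, continuous outcomes.** GP sizes were 1 + negative binomial (mean 5, CV 1), with 50 GPs per arm and residual variance 1 − 0.6² = 0.64 split by the ICC. The true effect was zero. Each cell had 800 replicates, 50 imputations, a REML random-intercept analysis and Rubin's rules. Patients in GPs with no observed follow-up were left out of the GP-dummy runs. Entries are for 10 / 20 / 35% missing.

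| | ITT SE over complete-case SE | ITT SE over true spread of the ITT estimate | Predictive mean matching with GP dummies, SE ratio |
|---|---|---|---|
| QoL | 1.10 / 1.21 / 1.38 | 1.08 / 1.18 / 1.29 | 1.08 / 1.17 / 1.30 |
| Burden | 1.07 / 1.13 / 1.24 | 1.04 / 1.09 / 1.20 | 1.05 / 1.10 / 1.19 |
| NPI | 1.04 / 1.08 / 1.15 | 1.04 / 1.07 / 1.13 | 1.03 / 1.06 / 1.11 |

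The ICC read by the QoL analysis rises from 0.06 to 0.10 / 0.14 / 0.23. Coverage of nominal 95% intervals for QoL is 95 / 98 / 99%. Random-intercept imputation gives SE ratios of 1.00 to 1.01 and coverage of 94 to 95% in every cell. Predictive mean matching on the same GP terms shows nearly the same inflation, so the planned sensitivity analysis cannot reveal it.

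**Step 4: drop-out that depends on baseline.** Section 2.3.2.2 requires that "the missing of the outcome variable is stochastically independent from the value of the outcome variable at follow-up given its baseline value". Within that condition (22% missing, opposite slopes by arm), bias is at most 0.005 for both imputation models, and the fixed-effect SE ratio is 1.23 / 1.15 / 1.09 (QoL / burden / NPI). In a separately coded simulation with 25% missing dependent on baseline, one-sided 0.05 power for a difference of 0.25 was, fixed-effect against random-intercept imputation, 73% v 84% (QoL), 64% v 75% (burden) and 56% v 63% (NPI).

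**Step 5: effect on p-values.** Take a complete-case one-sided p of 0.010 (z = 2.326; Bonferroni 5 × 0.010 = 0.050) and the same estimate in the ITT analysis at 20% missing:

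- QoL: 2.326/1.21 = 1.92, p = 0.027, Bonferroni 0.136
- Burden: 2.326/1.13 = 2.06, p = 0.020, Bonferroni 0.099
- NPI: 2.326/1.08 = 2.15, p = 0.016, Bonferroni 0.078

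**Step 6: binary outcomes.** At 10 / 20 / 35% missing (200 replicates, 20 imputations, missing completely at random):

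- 26 / 27 / 31% of GPs with data have one observed patient.
- 47 / 49 / 53% of GPs are all 0 or all 1.
- 28 / 30 / 37% of the people to be imputed sit in such GPs or in GPs with no observed follow-up.

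A direct maximum-likelihood fit (prevalence 25%, 25% missing) had 50 diverging GP coefficients, and the information matrix became singular.

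Four possible devices were compared: impute the GP's constant value, leave such patients unimputed, low-weight augmentation, or one pooled intercept per arm. Across them, the mean log odds ratio (true 0.6) shifts from complete case by −0.004 to +0.019 / −0.023 to +0.036 / −0.001 to +0.154. The SE ratio is 1.05–1.10 / 1.11–1.21 / 1.19–1.48. Monte Carlo error of the shifts is at most 0.010 (0.016 for the constant-value device at 35%). At 20% missing, prevalence 15% gives shifts of −0.050 to +0.038, and ICC 0.15 gives −0.017 to +0.054. Random-intercept logistic imputation shifts by at most 0.006, with SE ratios of 1.01 / 1.02 / 1.04.

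**Step 7: GPs with no observed follow-up.** These are about 3 / 6 / 11% of GPs.

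**The case against.** The strongest counter-argument is robustness. The ITT analysis exists to control attrition bias, and the SAP itself expects GPs to differ in adherence. If drop-out depends on the GP effect in one arm only (assumed log-odds slope 1 per SD, 21% missing), bias for QoL / burden / NPI is −0.002 / −0.014 / −0.027 with GP dummies. With random-intercept imputation it is −0.026 / −0.042 / −0.053, the same as complete case. Coverage is 96–98% against 93–94%. This stands, but it lies outside the missingness condition the SAP states, and root mean squared error is close (0.098 / 0.113 / 0.132 against 0.097 / 0.117 / 0.138). It justifies keeping GP dummies as a sensitivity analysis.

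Other points:

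- **Not every separated GP matters.** One with nobody to impute affects no imputed value. In a simulation under similar assumptions, about 11 / 19 / 28 of 100 GPs were separated and also held a patient to impute (13 / 25 / 40 with empty GPs added). The people concerned are about 3 / 6 / 13% of the sample. This stands as a limit on size; the stated fit still has no finite solution.
- **Software may return values** by dropping GPs, augmenting or penalising. True, but the SAP names none of these. At 10% missing the resulting shifts are barely above simulation noise. Predictive mean matching on linear predictions would avoid separation, but the SAP does not say it is linear, and it is only the sensitivity analysis.
- **The ranking of outcomes is conditional.** Burden and NPI depend on caregivers, so their missing rates may differ from QoL. NPI at 35% missing (1.15) exceeds QoL at 10% (1.10).
- **Type I error.** At 25% missing, one-sided 0.05 error was 5.8 / 6.3 / 5.3% with random-intercept imputation and 2.9 / 3.8 / 4.4% with GP dummies. The complete-case model gave 5.9 / 6.1 / 5.5%, so the replacement behaves like the SAP's own analysis model.
- **Harm is limited.** The departure is disclosed, the trial is called exploratory and the continuous error is conservative. All of this is accepted.

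**Conclusion.** The concern holds and should be fixed. Following section 2.3.2.2 exactly gives ITT standard errors that exceed the complete-case ones by 4 to 10% at 10% missing, 8 to 21% at 20% and 15 to 38% at 35%. The excess is largest for quality of life and smallest for NPI, provided missing rates are equal across outcomes and the Table 1 ICCs carry over. It comes from the imputation model, not from lost information.

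For antidementia drugs and PIM, the stated logistic model has no finite solution for roughly half of the GPs. The result then depends on an unstated device: slightly at 10% missing, by up to 0.154 on the log odds ratio at 35%. These sizes rest on assumed prevalence, ICC and missing rates; the separation itself does not.

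Under the SAP's missingness condition, point estimates for the continuous outcomes are not materially biased and the complete-case model remains valid. The planned step "Standardized effect sizes will be also computed from these imputations and compared to the estimates of the per protocol analyses" is therefore little affected for those outcomes. The damage is to the ITT intervals and p-values.

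**What to change.** In SAP section 2.3.2.2, replace "with the difference that the GP will be included as a fixed effect in the imputation model" with: *with the GP included as a random intercept and the study group as a fixed predictor (two-level multiple imputation, linear for quality of life, caregiver burden and NPI, logistic for antidementia drugs and PIM; 50 imputations)*.

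In section 2.3.2.4, base predictive mean matching on predictions from that same model, and add: *For the three continuous outcomes, linear imputation with GP as a fixed effect is kept as a labelled sensitivity analysis for drop-out that depends on the GP. Its standard errors are reported as conservative, and patients in GPs with no observed follow-up are left out of it and counted.*

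A random intercept also yields imputations for separated and empty GPs without an ad hoc rule. The cost is wording in two sections, a two-level imputation routine, longer run time and a convergence check; no new data are needed. With the same covariates, the corrected ITT analysis will largely reproduce the complete-case result, and it gives up some protection against GP-dependent drop-out, which the retained sensitivity analysis covers for the continuous outcomes.

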### **2.3.1.4 Secondary Analyses**

In secondary analyses, the above described statistical modelling will be performed stratified for the living situation (living alone vs. not living alone). As the intervention targets also the care-giver and

the social context of a person suffering from dementia, it is very plausible that the effects of the intervention are different for persons living alone and persons living not alone. For example, the caregiver burden might response differentially to the intervention. Thus, effect sizes of the intervention for the efficacy endpoints will be derived once for persons living alone and once for persons not living alone. Additionally, to allow an inference-statistical assessment, a study-group living status interaction term will be introduced in the models explained above. A significant interaction term will be interpreted correspondingly that the intervention does not have the same effect for individuals living alone and individuals living not alone.

Moreover, several subgroup analyses regarding differential treatment effects are planned following the workflow of the described stratification living alone vs. not living alone. The subgroups under consideration will be:

- 1) Moderate/severe vs. Mild dementia
- 2) Men vs. Women
- 3) Age under 80 vs Age above 80

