### **2.3.2.5 Secondary Analyses (ITT)**

The same analyses will be carried out as described in the per protocol analyses with the difference that missing values in the outcome variable at follow-up will be imputed.

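### If applied as listed, the ITT imputation model omits the study-group-by-subgroup terms and dementia severity, so ITT interaction estimates shrink by roughly the missing fraction

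*SAP*

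**What the plan says.** Section 2.3.2.2 of the SAP states an aim and then a list. The aim: "The imputation model will be chosen congenial to the analyses model with the difference that the GP will be included as a fixed effect". What is drawn from it is a linear regression for the three metric endpoints and a logistic regression for the two medication endpoints, "including the respective baseline variable, age, sex, the living status and the study group variable as predictors". Apart from the GP term, these are the predictors of the primary model in section 2.3.1.2.

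Section 2.3.2.4 adds a sensitivity run in which "the imputation models (including the same variables as before) will be based on predictive mean matching". Section 2.3.2.5 repeats the complete-case secondary analyses "with the difference that missing values in the outcome variable at follow-up will be imputed". Neither section changes the predictor list.

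Those secondary analyses are set out in section 2.3.1.4. For living status, "effect sizes of the intervention for the efficacy endpoints will be derived once for persons living alone" and once for the others, and "a study-group living status interaction term will be introduced in the models explained above". The same workflow applies to "Moderate/severe vs. Mild dementia", to sex and to age either side of 80. A significant interaction is to be read as a differing intervention effect.

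**The concern.** An imputation model without a study-group-by-subgroup term assumes that the intervention effect is the same in both strata. Observed patients carry whatever differential effect exists; imputed patients carry none. Testing the interaction on the combined data mixes the two, so the estimate moves towards zero and the stratum effects move towards each other. A stratum with no true effect then shows part of the other stratum's effect.

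At stake is the reading of the ITT subgroup results. Section 2.3.1.4 calls a different effect by living status very plausible and attaches an interpretation to the interaction test. With the listed model, ITT results would lean towards no differential effect. A gap between ITT and complete-case results could be put down to attrition when the imputation model had caused it.

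**Working it through.** The SAP gives no drop-out rate, interaction size or expected attenuation, so it has no figure of its own to reproduce here.

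**Terms needed against terms listed**

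| Analysis in 2.3.1.4 | Subgroup variable in list? | Interaction with study group in list? |
|---|---|---|
| Living status | yes | no |
| Dementia severity | no | no |
| Sex | yes | no |
| Age 80 | age, but not the cut | no |

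GP as a fixed effect does not fill the gap. Whole GPs are randomised, so the GP terms absorb the study-group main effect but do not let it differ between patients of the same GP.

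**Expected size.** Let m be the missing fraction and b the true interaction. Observed cases carry b and imputed cases about 0, so the estimate is about (1 − m)·b + m·0 = (1 − m)·b. With an assumed b = 0.40 SD and m = 20/30/40%, this gives 0.8 × 0.40 = 0.32, 0.7 × 0.40 = 0.28 and 0.6 × 0.40 = 0.24.

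For stratum effects, assume half the patients live alone and true effects of 0 and 0.40, so the average is 0.20. The null stratum becomes m × 0.20 = 0.04/0.06/0.08. The other becomes 0.40 − m × 0.20 = 0.36/0.34/0.32.

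**Simulation, linear endpoints.** From section 2.5: 100 GPs, mean cluster size 5, cluster-size variation coefficient 1, baseline–follow-up correlation 0.6, and ICCs of 0.061, 0.192 and 0.361. Assumed: outcomes missing completely at random, interaction 0.40 SD, 50% living alone, 40% moderate/severe, 60% women, about 50% over 80. Analysis: random-intercept model, 50 imputations with GP fixed effects, 400 simulated trials per cell (300 for predictive mean matching). The Monte Carlo standard error of the listed-model estimates is about 0.006.

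| Mean interaction estimate (true 0.40) | 20% missing | 30% | 40% |
|---|---|---|---|
| Complete case, living status, ICC 0.061 | 0.39 | 0.41 | 0.39 |
| Listed model, living status, ICC 0.061 | 0.31 | 0.27 | 0.21 |
| Listed model, living status, ICC 0.192 | 0.31 | 0.27 | 0.22 |
| Listed model, living status, ICC 0.361 | 0.31 | 0.26 | 0.22 |
| Listed model, severity | 0.31 | 0.28 | 0.22 |
| Listed model, sex | 0.31 | 0.27 | 0.23 |
| Listed model, age 80 | 0.32 | 0.27 | 0.23 |
| Listed variables, predictive mean matching | 0.32 | 0.27 | 0.23 |
| Imputed by study group, living status, ICC 0.061 | 0.39 | 0.40 | 0.38 |

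Stratum effects on the listed imputed data were 0.05/0.06/0.09 for a true 0 and 0.36/0.34/0.31 for a true 0.40, close to the hand calculation.

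**Dependence on method.** For living status at ICC 0.061, the share of the interaction kept above is 0.31/0.40 = 0.78, 0.27/0.40 = 0.68 and 0.21/0.40 = 0.53. Separately programmed runs gave 0.76/0.68/0.54, 0.78/0.68/0.57 and 0.83/0.72/0.64. The last used least squares without a GP random intercept, ICC 0.06 and a true interaction of 0.30. The loss is therefore 17–24%, 28–32% and 36–47% at 20, 30 and 40% missing. With missingness differing by arm and subgroup (about 30% on average, least squares), 0.73 was kept for living status and 0.72 for severity. With the interaction added to the imputation model, these separate runs recovered 97–104% of it.

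**Logistic endpoints.** With an assumed log-odds interaction of 1.0: complete case 1.02/1.02/1.06, listed model 0.83/0.74/0.67, interaction included 1.02/1.03/1.09. This is one set of runs with 10 imputations. It needed augmentation because 42–44 of 100 GPs had identical observed outcomes, so it supports the direction and only an approximate size.

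**The case against.** The strongest reply is that congeniality is the rule and the list only its application to the primary model. Applied to each interaction model, the rule would require the tested term. Since section 2.3.1.4 speaks of stratified modelling, imputing within strata is also a possible reading. Under either, the shrinkage does not arise. This stands as a limit: the point holds only for the list as written. But the list is presented as what congeniality implies, section 2.3.2.4 reuses it, and nothing extends it, so the literal reading is the natural one.

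The consequence is also limited. The trial is described as exploratory, the affected analyses are secondary, and the complete-case interactions are still reported without this shrinkage. The tests are weak in any case. For an interaction of 0.26 SD, the simulated complete-case standard errors of 0.163/0.174/0.189 give power Φ(0.26/SE − 1.96) of about 36/32/28% at an assumed two-sided 5%. All this stands and keeps the point below the level of the primary analysis. It does not excuse a second set of subgroup results biased in a known direction. The 40% figures vary between methods and should not be quoted as precise.

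A reader might infer that the primary ITT effect is biased by the same route. The documents do not support that: the list matches the primary model's predictors, and the primary model tests no interaction. A reader might also take the sentence in section 2.3.2.1, "The attrition bias caused by drop-out between the measurement points will be controlled by the imputation", as an unconditional claim that the ITT analysis fails to honour. Section 2.3.2.2 names the missingness condition as a prerequisite, so that is at most loose wording.

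**Conclusion.** The point holds in conditional form. If the predictors in section 2.3.2.2 are used as listed, the ITT interactions in section 2.3.2.5 are biased towards zero on the three linear endpoints by roughly the missing fraction, about 20–45% at 20–40% missing. Stratum effects converge, and predictive mean matching would not reveal it. The two logistic endpoints go the same way by an approximate amount.

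The direction follows from the listed model. The size rests on assumed drop-out, interaction size and subgroup prevalences, none of which the SAP gives. With an interaction of 0.40 SD on living status, ICC 0.061 and an assumed two-sided 5% test, simulated power falls from 70% to 44% at 20% missing and from 65% to 31% at 30% (complete case against listed imputation). The plan should be corrected here, but its primary conclusions do not depend on it.

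**What to change.** In section 2.3.2.2, with a reference from 2.3.2.4 and 2.3.2.5, add:

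> For each secondary analysis the imputation model also includes the tested subgroup variable (including baseline dementia severity and the under/above 80 indicator) and its interaction with study group, or imputation is done separately by study group with the subgroup variable as predictor. Predictive mean matching uses the same extended model.

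This needs no new data collection, only wording and computing time. The price is a larger imputation model and somewhat wider standard errors. Imputing by study group gave interaction standard errors of 0.172/0.189/0.213 at 20/30/40% missing, against 0.163/0.174/0.189 for complete cases (ratios 1.06/1.09/1.13), and power of 64% and 57% at 20 and 30% missing. The change brings the ITT interactions back into line with the complete-case ones; it does not make them more powerful. It neither causes nor solves the separate difficulty that a GP fixed effect cannot be estimated where no follow-up outcome is observed (about 6/9/14 of 100 GPs in the simulation).
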